### 6.3 Exclusion Criteria

Patients who meet any of the following exclusion criteria will be excluded from the study:

#### Main Criteria for Exclusion:

1. Pregnant or nursing (breastfeeding) women.
2. Receipt of any dose of a potentially therapeutic antibacterial agent (with potential activity against uropathogens in the urinary tract) from 72 hours prior to randomization until the first dose of test article. [NOTE: Subjects who developed the current pyelonephritis while receiving prophylactic antibacterial therapy (for any reason) may be eligible if all prophylactic antibacterials are stopped (no further dosing after randomization) and approved by the study medical monitor.]
3. Anticipated need for systemic antibacterial therapy other than test article (for treatment or prophylaxis) during the study period.
4. Infection at baseline that in the Investigator's judgment would require more than 10 days of antibacterial therapy (subjects determined to have bacteremia based on blood cultures collected at screening can be treated for up to 14 days).
5. Symptoms of AP present longer than 7 days prior to randomization.
6. Confirmed or suspected AP caused by a pathogen that is resistant to tetracyclines or fluoroquinolones, including infection caused by fungi (eg, *Candida* spp.) or mycobacteria (eg, urogenital tuberculosis).
7. Known or suspected rapidly-progressing or life-threatening illness including septic shock. Septic shock can be identified using the clinical criteria of hypotension requiring vasopressor therapy to maintain mean arterial blood pressure of 65mmHg or greater and having a serum lactate level greater than 2 mmol/L after adequate fluid resuscitation.
8. Use of an indwelling urinary catheter, nephrostomy tubes or other indwelling urinary tract device within the 30 days prior to randomization.
9. Confirmed or suspected urinary retention ( $\geq 100$  mL of residual urine after voiding) from any cause, including neurogenic bladder or obstruction.
10. History of surgically modified or abnormal urinary tract anatomy (eg, bladder diverticula or redundant urine collection system).
11. Confirmed or suspected complete or partial obstruction of the urinary tract, or obstructive uropathy that is scheduled to be medically or surgically relieved during the study therapy period (eg, renal calculi, urethral or ureteral stricture).
12. Confirmed or suspected renal disease or condition that, in the opinion of the investigator, may confound the assessment of efficacy, including but not limited to the following:
  - Perinephric or intrarenal abscess
  - Emphysematous pyelonephritis
  - Chronic pyelonephritis, including xanthogranulomatous pyelonephritis
  - Polycystic kidney disease
  - Renal carcinoma

13. History of renal transplant or a surgically created intestinal conduit for urinary diversion.
14. Suspected or confirmed non-renal source of infection (eg, prostatitis, epididymitis, orchitis, endocarditis, osteomyelitis, abscess, meningitis, pneumonia).
15. Confirmed or suspected vaginitis or sexually transmitted infection or lower UTI (ie, cystitis) without symptoms/signs of acute pyelonephritis.
16. Has any of the following at Screening:
  - alanine aminotransferase (ALT) or aspartate aminotransferase (AST)  $\geq 3 \times$  Upper Limit of Normal (ULN)
  - total bilirubin  $> 1.5 \times$  ULN
  - suspected or confirmed clinical evidence of end-stage liver disease (eg, ascites, hepatic encephalopathy)
17. History of unstable cardiac disease (eg, unstable angina, myocardial infarction, acute congestive heart failure, unstable cardiac arrhythmia, etc.) within the 3 months prior to randomization.
18. Significant immunological disease determined by any of the following:
  - Current or anticipated neutropenia defined as less than 500 neutrophils/mm^3
  - Known infection with Human Immunodeficiency Virus (HIV) and a cluster of differentiation 4 (CD4) count that is unknown or documented to be less than 200 cells/mm^3 within the last year, or other Acquired Immune Deficiency Syndrome (AIDS)-defining illness as determined by the investigator.
19. Receipt of cancer chemotherapy, radiotherapy, or potent, non-corticosteroid immunosuppressant drugs (eg, cyclosporine, azathioprine, tacrolimus, immune-modulating monoclonal antibody therapy, etc.) within the 3 months prior to randomization, or the receipt of systemic corticosteroids equivalent to or greater than 40 mg of prednisone per day (see equivalent corticosteroid doses in [Appendix 2](#)) or 40 mg of prednisone per day for more than 14 days in the 30 days prior to randomization.
20. History of hypersensitivity or allergic reaction (eg, anaphylaxis, urticaria, other significant reaction) to any tetracycline (eg, minocycline, doxycycline or tigecycline) or fluoroquinolone (eg, levofloxacin, ciprofloxacin, moxifloxacin) antibiotic.
21. Inability to swallow 6 tablets in succession.
22. History of pseudotumor cerebri, or prior (within 2 weeks prior to randomization) or planned concomitant use of isotretinoin.
23. History of systemic lupus erythematosus or lupus-like syndrome.
24. Has current evidence of pancreatitis.
25. History of myasthenia gravis.
26. Screening calculated creatinine clearance (CrCl)  $< 50$  mL/minute, using the Cockcroft-Gault equation (see equation in [Appendix 2](#)), requires any form of dialysis (eg, hemodialysis, peritoneal dialysis, or continuous veno-venous hemofiltration), or other evidence of severe renal disease.
27. History of tendinitis, tendon rupture, arthralgia, myalgia, peripheral neuropathy, or central nervous system effects (eg, hallucinations, anxiety, depression, insomnia, severe headaches, and confusion). \*
28. Has a QT interval  $> 500$  msec, or known long QT syndrome. \*
29. Current use of antiarrhythmic agents of Class IA (eg, quinidine, procainamide) or Class III (eg, amiodarone, sotalol). \*

30. Use of other investigational drugs within 5 half-lives or 30 days prior to randomization, whichever is longer.
31. Has previously been treated with omadacycline or previously enrolled in this study.
32. Unable or unwilling, in the opinion of the investigator, to comply with the protocol requirements, or has any concomitant condition or planned medical intervention that, in the opinion of the investigator, is likely to interfere with evaluation of the response of the infection under study, determination of AEs, or completion of the expected course of treatment.

\* Exclusions required due to fluoroquinolone comparator

#### **6.4 Screen Failures**

Subjects who sign the ICF but withdraw or are withdrawn from the study before random assignment to double-blind treatment are defined as screen failures. All screen failures should be recorded on the subject master list. Limited information including reason for screen failure will be recorded on the electronic case report form (eCRF) or interactive voice/web response system (IxRS) system for screen failures. Screen failure subjects may be re-screened at the discretion of the investigator and in consultation with the medical monitor as needed. A subject who discontinues participation or is withdrawn before receiving a treatment assignment, and who is re-screened at a later time will be assigned a new subject number and recorded as re-screened

Omadacycline  
PTK0796-AP-17202-Version 1.0; 26Mar2018

Paratek Pharma, LLC.  
IND # 75,928 IND # 73,431

## 7 STUDY TREATMENT(S)

### 7.1 Treatments Administered

Test articles will be supplied by Paratek Pharma, Inc (the sponsor). Test articles will be labeled according to regulations.

The test articles should be administered only to subjects who have provided informed consent and who meet all of the inclusion criteria and none of the exclusion criteria. Once the test article has been assigned to a subject, it must not be reassigned to another subject.

Following a Screening period of up to 24 hours, eligible subjects will be randomly assigned to receive iv or iv/po dosing regimens of omadacycline treatment or an iv/po regimen of levofloxacin. Intravenous treatment will be double-blind and oral treatment will be double-blind and double-dummy.

### 7.2 Identity of the Investigational Product: Omadacycline

#### Intravenous Formulation (Omadacycline)

Name	Omadacycline
Excipients	Tosylate acid counter ion, sucrose, hydrochloric acid and sodium hydroxide to adjust the pH
How supplied	Sterile, lyophilized powder for reconstitution packaged in a clear, glass vial with a rubber stopper and aluminum overseal. The labeled content of the vial is 100 mg of omadacycline base. There is a 4% overfill to allow for the extraction of a 100 mg dose.
Storage	Store at 25°C (77°F). Excursions permitted to 15°C to 30°C (59-86°F)
Preparation and handling	To prepare the 100 mg dose, add 5 mL of the reconstituted solution (the content of one 100 mg vial) to the infusion container 150 mL Normal Saline (NS).  To prepare the 200 mg dose, add 10 mL of the reconstituted solution (the contents of two 100 mg vials) to the infusion container of 150 mL NS. The prepared infusion solution should be used within 8 hours or stored at up to 24 hours at 2°C to 8°C (36°F to 46°F). Please refer to the Pharmacy Manual for additional information.
Administration	Please reference Table 2 in Section 7.6.6.1

Omadacycline  
PTK0796-AP-17202-Version 1.0; 26Mar2018

Paratek Pharma, LLC.  
IND # 75,928 IND # 73,431

### Oral Formulation (Omadacycline)

Name	Omadacycline Tablet, 150 mg
Excipients	Lactose monohydrate, microcrystalline cellulose, sodium stearyl fumarate, crospovidone, colloidal silicone dioxide, sodium bisulfite, polyvinyl alcohol, titanium dioxide, talc, glycerol monocaprylocaprate, sodium lauryl sulfate, iron oxide yellow
How supplied	High-Density Polyethylene (HDPE) bottles with induction seal, child resistant closure and desiccant
Storage	Store at 25°C (77°F). Excursions permitted to 15°C-30°C (59-86°F) (Per Pharmacy Manual)
Preparation and handling	No special requirements
Administration	Please reference Table 2 in Section 7.6.6.1

### 7.3 Comparator Test Article: Levofloxacin

#### Intravenous Formulation (Levofloxacin)

Name	Levofloxacin
Excipients	Sodium chloride, sodium hydroxide (for pH adjustment), hydrochloric acid (for pH adjustment), and water for injection
How supplied	Levofloxacin 5 mg/ml in saline. Single-Use premixed solution in container for intravenous infusion.
Storage	Store at 25°C (77 °F) or below. Do not freeze or refrigerate
Preparation and handling	Transfer 150 mL of solution into an evacuated container. Please refer to Pharmacy Manual for additional information.
Administration	Please reference Table 2 in Section 7.6.6.1

#### Oral Formulation (Levofloxacin)

Name	Levofloxacin Tablet, 250 mg
Excipients	Over encapsulated in DB0, Swedish Orange capsule shell with microcrystalline cellulose backfill.
How supplied	High-Density Polyethylene (HDPE) bottles with induction seal, child resistant closure and desiccant
Storage	Store at 25°C (77 °F). Excursions permitted to 15°C-30°C (59-86°F) (In Pharmacy Manual)
Preparation and handling	No special requirements
Administration	Please reference Table 2 in Section 7.6.6.1

## 7.4 Dose Selection Rationale

The dosing regimen of omadacycline selected for this study is based on the nonclinical and clinical experience to date, including *in vitro* antibacterial activity, PK characteristics, clinical efficacy in prior studies, and the overall safety and tolerability profile. Key considerations in dose selection are summarized below:

- In PTK0796-SDES-0501, the PK of omadacycline iv were linear over the entire dose range (25 mg to 600 mg) as assessed by area under the concentration time curve (AUC). Therefore, the loading dose given on Day 1 in the pivotal Phase 3 trials, 100 mg iv every 12 hours (q12h), is from an exposure perspective comparable to the 200 mg iv loading dose on Day 1 to be utilized in this study.
- In PTK0796-MDES-0601, 200 mg iv for seven days was safe and well tolerated. Alanine aminotransferase was reported as increased in 26% of subjects however the post-baseline change was approximately 30 IU/L on the last day of infusion. A heart rate model demonstrated that the post-baseline increase in heart rate for a 200 mg dose could be minimized to 15 beats per minute with infusion over 60 minutes.
- In PTK0796-UUTI-15103, omadacycline dosed as 200 mg iv on Day 1 followed by 300 mg po daily for 5 days, 300 mg po q12h on Day 1 followed by 300 mg po daily for 5 days and 450 mg po q12h on Day 1 followed by 450 mg po daily for 5 days demonstrated high urinary concentration on Day 1 and Day 5. For the 200 mg iv load followed by 300 mg daily dosing group, mean urinary concentrations ranged from 22 to 65 µg/mL on Day 1 and 21 to 42 µg/mL on Day 5. For the 300 mg dosing group, mean urinary concentrations ranged from 14 to 20 µg/mL on Day 1 and 17 to 30 µg/mL on Day 5. For the 450 mg dosing group, mean urinary concentrations ranged from 11 to 25 µg/mL on Day 1 and 30 to 48 µg/mL on Day 5.
- The driver of efficacy for omadacycline in urinary tract infection (UTI) is not known, however the extensive tissue distribution of omadacycline suggests that plasma levels may not be the best predictor of efficacy for every indication. Extensive tissue distribution is likely essential for the eradication of susceptible bacteria in the intracellular compartment of peripheral tissues. In the BAL-15104 study examining lung tissue concentrations following iv administration of 100 mg omadacycline in healthy subjects, at steady-state, the concentration of omadacycline was 25.79-fold higher in alveolar cells (AC, 302.46 h·µg/mL) than in plasma, and 1.47-fold higher in epithelial lining fluid (ELF, 17.23 h·µg/mL) than in plasma.
- A pragmatic assumption was made in the recently completed Phase 1 study of uncomplicated UTI (PTK0796-UUTI-15103) that maximizing the time of omadacycline concentration in urine above the pathogen MIC (ideally, throughout the dosing interval) would be desirable. In addition, the omadacycline concentrations in urine determined in the phase 1 study demonstrated that the urine concentrations were above the *E. coli* MIC90 of 2 µg/mL. It is appropriate to determine the optimal iv and oral dose for AP to achieve clinical success similar to a standard comparator. Therefore, both the standard 100 mg iv dose as well as the higher 200 mg iv dose will be explored. Oral doses of 300

Omadacycline  
PTK0796-AP-17202-Version 1.0; 26Mar2018

Paratek Pharma, LLC.  
IND # 75,928 IND # 73,431

mg and 450 mg will be explored as was done in PTK0796-UUTI-15103 and is being explored for the uncomplicated UTI (acute cystitis) in PTK0796-UUTI-17201.

## 7.5 Description of Treatments

Subjects will be randomized to 1 of the following 5 treatment groups:

**Table 1. Description of Treatment Groups**

Group	Test Article	Study Day 1	Study Days 2 to 7	Study Days 8 to 10 a
1	omadacycline	200 mg iv	200 mg iv	200 mg iv
2	omadacycline	200 mg iv	100 mg iv	100 mg iv
3	omadacycline	200 mg iv	300 mg po or 100 mg iv	300 mg po or 100 mg iv
4	omadacycline	200 mg iv	450 mg po or 100 mg iv	450 mg po or 100 mg iv
5	levofloxacin	750 mg iv	750 mg po or 750 mg iv	750 mg po or 750 mg iv

Dosing in all treatment groups is once-per-day.

All iv doses will be administered as continuous infusions over 90 minutes.

All oral doses will be taken in a fasted state (no food, antacids or multivitamins containing multivalent cations [eg, aluminum, magnesium, calcium, bismuth, iron, or zinc] or drink except water for at least 6 hours prior to dosing; after dosing, no food for 2 hours, no dairy products, antacids or multivitamins containing multivalent cations for 4 hours).

iv = intravenous, po = per oral.

a The total duration of treatment for subjects is 7-10 days, up to 14 days of treatment for subjects with bacteremia.

It is possible that not all treatment arms will be enrolling subjects at the same time. Arms may be dropped based on the Bayesian analysis or initiated based on the Bayesian analysis of the ongoing treatment arms. There will always be at least one omadacycline arm and the levofloxacin arm open.

## 7.6 Test Article Administration

### 7.6.1 Intravenous Treatment Phase

The iv treatment phase (minimum 1 day, 1 dose) will follow a double-blind design for omadacycline and levofloxacin. Infusions of both test articles will be administered continuously over approximately 90 minutes. All infusion start and stop times are to be recorded in the source documents and on the eCRF. Because the color of the test article and placebo infusions are different, all infusion bags and iv tubing will be covered with materials provided by the sponsor (as described in the Pharmacy Manual) so that subjects and blinded study personnel will not know the identity of the test article being administered. Subjects in each study arm will receive the same infusion volumes with the same blinded administration instructions. All iv infusions will be administered by qualified blinded personnel. However, unblinded personnel may administer the iv infusions provided they will not be performing

any efficacy assessments. If gravity administration is not the standard of care then an infusion pump may be used. If an infusion pump is used then an unblinded administrator will be required.

### 7.6.2 Selection and Timing of iv Dose for Each Subject

To facilitate study enrollment at all times of the day and permit subjects to be “shifted” to a more practical dosing schedule consistent with hospital schedules, provision is made for limited adjustment of the dosing interval. Specifically, infusion times may be adjusted up to  $\pm 2$  hours per infusion interval until the desired administration schedule is achieved.

Once the desired start of infusion time is determined, subsequent infusions should be “anchored” to that time. That is, thereafter, the start of infusion should be within  $\pm 1$  hour of the specified target infusion time.

### 7.6.3 Management While on iv Test Article

While the subject is receiving iv therapy, the investigator will assess the subject daily and choose one of the following outcomes based on the overall clinical response of the subject:

- Continue iv test article
- Assess for po test article using the protocol defined criteria (after a minimum of 1 days [1 doses] of iv therapy), see [Section 7.6.5](#). Note, the first po dose should be administered in the morning, 12 to 24 hours after the last dose of iv test article.
- Discontinue test article – this decision will prompt the EOT evaluation (even if the subject does not complete the minimum of 7 days of dosing)

Subjects who meet the criteria and are switched to po test article administration will continue to receive iv infusions throughout their treatment phase in order to maintain the blind. Subjects randomized to an IV only treatment group will continue to receive active IV treatment and placebo po treatment. Subjects randomized to an IV/PO treatment group will receive placebo IV and active po treatment. At all times during the study the decision to continue iv, switch to po, or discontinue test article is made based on the clinical judgment of the investigator. Each daily decision is to be recorded on source documents and the information transferred to eCRFs by blinded study site personnel.

#### 7.6.4 Investigator's Decision to Continue or Discontinue Treatment

At all times during the study the decision to continue iv, switch to po, or discontinue test article is made based on the clinical judgment of the investigator. The investigator may use the culture and susceptibility results from the local microbiology laboratory to help guide therapy; however, decisions to continue or discontinue test article should be based on clinical response rather than susceptibility results (as omadacycline susceptibility testing is not available at the local site). If the AP is caused by a microorganism that is not susceptible to levofloxacin *in vitro*, the decision to continue or discontinue study treatment should be based on the subject's clinical course and the investigator's clinical judgment. These cases should be discussed with the Medical Monitor. The rationale for this decision should be recorded in source documents.

#### 7.6.5 Investigator's Decision to Switch from iv to po Treatment

Initially, all randomized subjects will receive at least 1 day of iv antibacterial therapy. Beginning on the day 2 visit, the subject may be eligible to switch from iv to po therapy.

Switch from active iv to active po study drug therapy is optional, and will occur based on treatment group assigned. Upon decision to switch, subjects randomized to iv only groups will begin to receive placebo po in addition to their active iv test article. Those in an iv/po group will begin to receive active po test article and placebo iv infusions. The decision should be made by the investigator based on evaluation of the criteria below. Criteria will be confirmed and documented in source documents:

- Afebrile for  $\geq 24$  hours (highest daily oral, tympanic, rectal, or core temperature  $< 37.8^{\circ}\text{C}$  [ $100.0^{\circ}\text{F}$ ]) without the use of anti-pyretics,
- Improvement or resolution of the signs and symptoms of the index AP,
- Ability to tolerate and ingest oral therapy (eg, no nausea, vomiting), and
- For subjects with baseline bacteremia, follow-up blood cultures must be negative.

Subjects who are switched to po test article administration will continue to receive iv infusions in order to maintain the blind. Switch to po will not be permitted until after the subject has completed at least the first day of iv treatment (after 1 dose). The date and time the investigator confirmed the criteria for the subject's eligibility for po treatment were met and made the decision to switch to po treatment will be recorded on source documents and the information transferred to eCRFs by study site personnel.

#### 7.6.6 Oral Treatment Phase

When switching from iv to po test article the recommended interval between doses will be maintained. The first po dose, for both omadacycline and levofloxacin treatment arms, should be given in the morning 12 to 24 hours after the last dose of iv test article.

The po treatment phase will employ a double-blind, double-dummy design using omadacycline placebo comparator tablets of matching size and shape to active omadacycline tablets and matching over-encapsulated placebo and active levofloxacin tablets.

To maintain investigator and subject blinding, subjects in both arms will receive both tablets and over-encapsulated tablets during each dose. Subjects in groups 1 and 2 will receive placebo omadacycline tablets and placebo over encapsulated levofloxacin tablets. Subjects in groups 3, 4 and 5 will also continue to receive iv placebo infusions to maintain the blind.

The po treatment will be administered by study staff during visit assessments.

All doses of oral test article should be taken with water.

All oral doses should be taken in a fasted state. Fasting is defined as no food, antacids or multivitamins containing multivalent cations (eg, aluminum, magnesium, calcium, bismuth, iron, or zinc) or drink except water for at least 6 hours before dosing. After dosing, no food is permitted for 2 hours as well as no dairy products, antacids or multivitamins containing multivalent cations (eg, aluminum, magnesium, calcium, bismuth, iron, or zinc) for 4 hours.

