**Table 2. Dosing Blinded iv and Oral Double-Blind, Double-Dummy Design**

Dosing		Group 1 omadacycline	Group 2 omadacycline	Group 3 omadacycline	Group 4 omadacycline	Group 5 Levofloxacin
Day 1		omadacycline 200 mg iv in 150 mL NS	omadacycline 200 mg iv in 150 mL NS	omadacycline 200 mg iv in 150 mL NS	omadacycline 200 mg iv in 150 mL NS	levofloxacin 750 mg iv in 150 mL saline
Days 2 to 7-10 a, b, c	continue iv	omadacycline 200 mg iv in 150 mL NS	omadacycline 100 mg iv in 150 mL NS	omadacycline 100 mg iv in 150 mL NS	omadacycline 100 mg iv in 150 mL NS	levofloxacin 750 mg iv in 150 mL saline
	switch to po b	omadacycline 200 mg iv in 150 mL NS and three placebo tablets resembling omadacycline and three over- encapsulated placebo tablets resembling levofloxacin	omadacycline 100 mg iv in 150 mL NS and three placebo tablets resembling omadacycline and three over- encapsulated placebo tablets resembling levofloxacin	150 mL NS and two 150 mg omadacycline tablets, one placebo tablet resembling omadacycline, and three over- encapsulated placebo tablets resembling levofloxacin	150 mL NS and three 150 mg omadacycline tablets and three over- encapsulated placebo tablets resembling levofloxacin	150 mL NS and three placebo tablets resembling omadacycline and three over- encapsulated 250 mg levofloxacin tablets

Dosing in all treatment groups is once-per-day.

All iv doses will be administered as continuous infusions over 90 minutes.

All oral doses will be taken in a fasted state (no food, antacids or multivitamins containing multivalent cations [eg, aluminum, magnesium, calcium, bismuth, iron, or zinc] or drink except water for at least 6 hours prior to dosing; after dosing, no food for 2 hours, no dairy products, antacids or multivitamins containing multivalent cations for 4 hours).

iv = intravenous, NS = normal saline, po = per oral.

a The total duration of treatment is 7-10 days, Subjects with bacteremia can continue treatment for up to 14 days.

b Starting on Day 2, per investigator's discretion, subjects may be switched to oral dosing per oral switch criteria.

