### **7.10 Blinding**

The investigator and sponsor will be blinded to treatment group assignments throughout the study. The sponsor designee (eg, study statistical team, IxRS vendor, etc.) will have a designated randomization administrator who will maintain the randomization codes in accordance with standard operating procedures to ensure the blind is properly maintained,

Omadacycline  
PTK0796-AP-17202-Version 1.0; 26Mar2018

Paratek Pharma, LLC.  
IND # 75,928 IND # 73,431

and that only sponsor personnel who require knowledge of treatment assignments will be unblinded (eg, staff involved in maintaining the randomization codes). The DMC will review safety data and the results from the Bayesian analysis of efficacy. Based on this analysis, modifications may be made to the omadacycline treatment groups.

The investigator and sponsor will be blinded to treatment arm assignments. The iv and po phases of the study will be double-blind.

Because the color of the iv test article infusions and placebo infusions differ, all infusion bags and iv tubing will be covered with materials provided by the sponsor so that subjects and blinded study personnel will not know the identity of the test article being administered. The infusion regimen will follow a blinded design with subjects in each study arm receiving the same infusion volumes with the same administration instructions. Blinded study personnel will administer the infusions and collect, review and enter data regarding the iv infusions (eg, start and stop times) into an eCRF. If gravity administration is not the standard of care then an infusion pump may be used. If an infusion pump is used then an unblinded administrator will be required. Personnel identified as unblinded administrators will not participate in any study procedures other than iv administration of test article and the collection, review and entry of iv related data (eg, start and stop times) into an eCRF.

During the po phase, a double-blind, double-dummy design will be used to ensure the blind is maintained. Subjects on the omadacycline arms may receive active omadacycline tablets and over-encapsulated levofloxacin placebo tablets. Subjects on the levofloxacin arm will receive omadacycline placebo tablets and over-encapsulated active levofloxacin tablets. Infusions will be administered concomitantly along with the po treatment to maintain the overall study blind.

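### The fixed 0–24 h urine pool can include a second active dose when a Group 3 or 4 subject switches to tablets on Day 4 or Day 7, less than 24 h after the last infusion

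*Protocol*

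**What the plan says.** - **Interval.** Protocol Table 2: "Dosing in all treatment groups is once-per-day". Protocol 7.6.6 says that at the switch "the recommended interval between doses will be maintained".
- **First oral dose.** The next sentence of 7.6.6 says it "should be given in the morning 12 to 24 hours after the last dose of iv test article". Protocol 7.6.3 repeats this: "Note, the first po dose should be administered in the morning, 12 to 24 hours after the last dose of iv test article".
- **When a switch can happen.** Protocol 7.6.5: "Beginning on the day 2 visit, the subject may be eligible to switch from iv to po therapy". One criterion is at least 24 h without fever.
- **Infusion times.** Protocol 7.6.2 lets the schedule move, its stated purpose being "To facilitate study enrollment at all times of the day". The limit is 2 h either way "hours per infusion interval until the desired administration schedule is achieved", then 1 h either side of the fixed target time.
- **Infusions after the switch.** They continue in every arm: active in Groups 1 and 2, placebo in Groups 3 to 5. Protocol 7.10: "Infusions will be administered concomitantly along with the po treatment to maintain the overall study blind".
- **Urine PK.** Protocol 8.11.2 pools all urine from 0 to 24 h after the Day 3 dose and again after the Day 6 dose. The data serve two purposes: a 24 h average concentration, and the quantity excreted per dosing interval at steady state. The section has no instruction to stop at the next dose.
- **PK records and analysis.** Protocol 8.11 records exact dosing times and actual sample collection times, and refers to separate site instructions. Protocol 12.1 places the PK analysis in its own plan, and the SAP excludes PK reporting.

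**The concern.** A gap of 12 h does not keep a 24 h interval, so the two sentences of 7.6.6 disagree as written. The practical consequence lies in the urine collection, which runs by the clock rather than to the next dose. In Groups 3 and 4 the switch-day tablets are active omadacycline. If they are taken before the 24 h collection has ended, the pool holds drug from two doses but is labelled as the amount from one interval.

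Omadacycline PK in this population is a secondary objective. Recorded dose times let an analyst flag or exclude such a pool, but the single-interval amount cannot be recovered once the urine is mixed. Only a collection rule at the site can preserve it.

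**Working it through.** **Inputs.** Dosing interval 24 h (Table 2). Gap from last infusion to first oral dose, g, 12 to 24 h (7.6.6, 7.6.3). Pool 0 to 24 h (8.11.2). Infusion shift at most 2 h per interval, or 1 h around a fixed target (7.6.2). Infusion length 90 min (Table 2). Urinary excretion 10% to 13% of an oral dose at steady state (Protocol 3.2). The plan gives no figure of its own to reproduce here.

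**Step 1. Part of the pool that follows the second dose.** Overlap = 24 − g.

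| Gap g (h) | Overlap (h) | Share of pool time |
|---|---|---|
| 12 | 12 | 50.0% |
| 16 | 8 | 33.3% |
| 20 | 4 | 16.7% |
| 22 | 2 | 8.3% |
| 24 | 0 | 0% |

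If the 12 h is counted from the end of the infusion, the start-to-start gap is 12 + 1.5 = 13.5 h. The overlap is then 10.5 h (43.8%).

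**Step 2. Can it arise?**
- Unshifted: infusion at 20:00 on Day 3, tablets at 08:00 on Day 4. The gap is 12 h. The pool runs to 20:00 on Day 4, so its second half follows the tablets. It reflects 100 mg iv plus 300 mg po in Group 3, or 100 mg iv plus 450 mg po in Group 4.
- Shifted: first infusion at 20:00, moved 2 h earlier each day, so 16:00 on Day 3. With morning taken as 06:00 to 12:00 (my assumption), the next morning is 14 to 20 h later and the overlap is 4 to 10 h.
- Same subject at Day 6: the infusion has reached 10:00. Tablets at 08:00 to 10:00 on Day 7 come 22 to 24 h later, so the overlap is at most 2 h. A large overlap in the Day 6 pool therefore mainly concerns subjects whose schedule was not shifted.

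**Step 3. Groups 1 and 2.** Their tablets are placebo, so only an infusion moved forward could add a second active dose. Under 7.6.2 the shortest start-to-start interval is 24 − 2 = 22 h while shifting and (24 − 1) − 1 = 22 h once fixed. The overlap is at most 2 h. It can occur in any subject, switched or not, so it does not come from the switch rule.

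**Step 4. Rough amount added in Groups 3 and 4 at g = 12 h.** Assume one compartment, no absorption delay and a half-life h of 12 to 36 h. The half-life is not in the documents. The fraction of the dose's urinary excretion that falls in its first 12 h is 1 − 2^(−12/h): 0.50 at h = 12 and 0.206 at h = 36.
- 300 mg: 300 × 0.10 × 0.206 = 6.2 mg to 300 × 0.13 × 0.50 = 19.5 mg.
- 450 mg: 450 × 0.10 × 0.206 = 9.3 mg to 450 × 0.13 × 0.50 = 29.25 mg.

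The documents give no urinary fraction for an iv dose, so this cannot be turned into a percentage of the correct amount.

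**The case against.** **The rules can be reconciled.** The phrase about maintaining the recommended interval does not define that interval, and the 12 to 24 h sentence can be read as supplying it, as a deliberate one-off for morning fasted dosing. Switching is optional, and 7.6.2 provides a way to move the schedule. This has force: as a dosing matter the wording is under-specified rather than unworkable. It does not help the urine pool, because the more clearly 12 h is permitted, the more clearly the pool can contain two doses.

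**A reader might infer a harder conflict.** If 7.10 means that tablets and infusion are given at the same clock time, the 7.6.2 limits would force at least 22 h between the last infusion and the tablets. Then 10 of the 12 h in the window would be unusable. If the infusion nevertheless moved with early tablets, all four omadacycline arms would have two-dose pools. The documents do not support this. Section 7.6.2 governs infusions only. The word used in 7.10 can equally mean that infusions continue during the oral phase, as 7.6.3 describes, and an active infusion moved by more than 2 h would breach 7.6.2. I therefore give no figure for Groups 1 and 2 beyond the 2 h limit.

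**It may already be handled.** Dosing and collection times are recorded, and the separate PK plan, the site PK instructions or the Pharmacy Manual may contain a stop rule. None was available to check. If one does, the PK point falls away. Recorded times alone permit exclusion of a pool, not its repair.

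**Few subjects are involved.** A two-dose pool needs a switch exactly on Day 4 or Day 7 after a late infusion. This stands.

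**Conclusion.** The point holds for Groups 3 and 4. When the first tablets are taken on Day 4 or Day 7 less than 24 h after the previous infusion, up to 12 h (50%) of the fixed pool follows a second active dose. The pool then does not measure the amount excreted in one dosing interval. At the 12 h extreme the excess is about 6 to 20 mg (Group 3) or 9 to 29 mg (Group 4), conditional on the assumed half-life.

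Severity is minor, and only the secondary PK objective is touched. The documents give no basis for counting affected subjects; the number is probably small. A reader might go on to infer an effect on efficacy or a bias between arms. Nothing in the documents shows either, and neither is claimed.

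**What to change.** In Protocol 8.11.2:
1. End each urine collection at 24 h or immediately before the next dose of test article (tablets or infusion), whichever comes first, under the same rule in all arms so that it does not reveal treatment.
2. Record the actual start and stop times, and report the amount over the actual interval.
3. Summarise pools clearly shorter than 24 h apart from the 24 h average concentration and amount. A cut-off at 22 h would fit, since 7.6.2 already allows that interval.

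**Cost.** No extra procedure and no change to dosing, but a written amendment with ethics approval (Protocol 13.6.2) and a note to sites. Affected pools may cover as little as 12 h and leave the 24 h summaries. Because the rule is common to all arms, some Group 1 and 2 pools would also be cut short at placebo tablets.

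**What not to do.** Do not settle the 7.6.6 wording by waiving the 7.6.2 limits on the switch day. That would newly authorise active infusions 12 h apart in Groups 1 and 2, that is 200 + 200 mg iv in Group 1. The multiple-dose support cited in 7.4 is 200 mg iv for seven days, with ALT increases reported in 26% of subjects.
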